Aim 2: To determine accuracy of the ratio of PIGF/sFlt-1 in predicting PET and the effect of metformin on this ratio

The objectives under this aim will include,

1. A comparison of the serum levels of the PIGF/sFlt-1 ratio measured in early pregnancy between non-PET and PET patients.
2. A comparison of the PIGF/sFlt-1 ratio PET in patients who received metformin versus standard care group.

Aim 3: To study the molecular mechanisms and signaling pathways associated with increased levels of sFlt-1 and PET.

Regarding aim 3: in response to the reviewer's comments, the study team has agreed to collect the blood sample and placenta from the patients and store them for future analysis.

4. Preliminary data or studies

Metformin safety in pregnancy

substantial evidence on the benefits of metformin an antihyperglycemic agent when pregnant women with gestational and Type 2 diabetes. In polycystic ovary syndrome

1 Jan - Revised On May 2017

Page 5 of 22

(PCOS) patients, it is known to decrease the risk of first trimester miscarriages and the incidence of gestational diabetes (48,49). In diabetic pregnancies, metformin has been associated with favorable maternal and neonatal outcomes (50,51). Observed maternal outcomes include less weight gain during pregnancy, better glycemic control, and reduced fat distribution (52). Other benefits include a reduction in pregnancy induced hypertension and PET, lower risk of neonatal hypoglycemia and ICU admission. Neonatal outcomes include: reduced fat around organs, which could result in improved insulin resistance and prevention of diabetes later in life (52). Even though metformin is known to cross the placenta, its use in early pregnancy or late pregnancy has not been shown to be associated with an increased risk of congenital malformation or adverse neonatal outcomes except a lower neonatal birth weight (53–56).

Metformin has been safely administered at the dose we propose to use here to diabetic patients. It has become the first line treatment of type 2 DM in pregnancy and poorly controlled gestational diabetes on diet based on the NICE guideline and the national diabetes guideline in Qatar. However, anticipated side effects include: GI disturbances such as gas (4-12%), heartburn, stomach pain (3-4%), nausea (7-9%), and GI changes. Serious side effects associated with its use are hypoglycemia and lactic acidosis which are extremely rare (<1%) (57).

Metformin in PET:

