Randomization and initiation of the study:

Once recruited, the patient data will be entered onto a web-based randomization software to determine study group and to the clinical trial management software, where a study ID number will be assigned. If the patient agrees to enter the trial, the site coordinator will contact the study physician to initiate study protocol (appendix 2) and then the patient will continue to be followed-up by her clinical team. In cases where patient assigned to control group and diagnosed with GDM and started on metformin, she will be moved to intervention group and analyzed as late started. If patient declined to participate initially, or dropped out from the study, all her data will be removed.

A clinical trial management software will be utilized to enter patient data. Each study Co-PI (physician) will lead a study site and supported by study coordinator. They will be responsible for reviewing patient eligibility, initiating the study protocol and patient counselling. They will meet regularly to share study updates. Study coordinators will be responsible for patient counselling, obtaining written informed consent, data collection and entry, and blood samples and placenta shipment from the study sites to study research laboratory at Sidra Medicine. The LPI will meet with the research team monthly to review various aspects of the trial to ensure conformation to the protocol and principles of GCP.

Collected data (appendix 5):

Variables to be collected include patient demographic characteristics, past medical and surgical history, past medication history, allergies, vital signs, CBC as routinely done and LFT, serum creatinine and biomarker serum level (sFlt-1, VEGF, PIGF). Blood samples will be collected by the phlebotomist or the responsible nurse. The blood investigations, 5 ml blood sample will be collected at baseline, second and third trimester and after delivery. The blood sample will be used for CBC, LFT, serum creatinine, and study serum biomarker in aim 2 (sFLT-1, VEGF, PIGF), and well as for storage for future DNA/RNA analysis for aim 3. Further, placenta samples will be collected and stored for future DNA/RNA analysis.

Medication adherence and adverse drug related events (ADRs):

Medication adherence is crucial to achieve the study objectives. Patient medication adherence is measured using the pill count method on each visit and Morisky scale (appendix 6) in

1st - Revised On May 2017

Page 12 of 22

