each visit or telephone call. Furthermore, to increase patient medication adherence, a reminder SMS will be send as well as three telephone calls to individual patient on regular basis. Adverse drug reaction (ADRs) will be reported using [name] Medical Corporation ADR form (Appendix 7) to both DSMC and MRC when they occur, however, serious ADRs will be reported within 48 hours by the study PI.

6. Sample size and calculation

Our sample size calculation was based on Syngelaki A. et al. (2016) findings. In this study, obese patient where either randomized to metformin or placebo to see the effect on neonatal birth weight. As a secondary outcome, metformin use was associated with 76% reduction in PET (3% versus 11.3% respectively, OR 0.24, 95% CI 0.10 – 0.61, $P = 0.001$).

We expect that for a study power of 80% and to detect a reduction at a level of 5% significance, with considering above outcome estimates it is approximately estimated to be 172 patients in each arm, for a total of 344 in both group based on 1:1 ratio. Allowing for a maximum 20% dropout, we estimate that 414 patients would need to undergo randomization, to give 207 patients in each group.

7. Data collection methods and procedure

These will be at baseline, in the second and again in the third trimesters. The data to be collected include patient clinical information, blood sample and placental tissue (appendix 5). At each study visit 5 ml maternal venous whole blood will be collected by a laboratory phlebotomist or a nurse (one at baseline, and one at each following trimester/visit and admission/s, see appendix 2) for all included subjects. The blood sample will be used for measuring blood markers for aim 2 and stored for future DNA/RNA analysis for aim 3. In addition, placental tissue will be collected and stored for future DNA/RNA analysis. In brief:

- (a) Baseline Data (Week 11⁺⁰ to 13⁺⁶): Patient sociodemographic data including age and ethnicity, Obstetrical, medical, surgical and medication history, current pregnancy information, CBC, as routinely done and study biomarkers of LFT, serum creatinine, sFlt-1, VEGF and PIGF.
- (b) Second (week 19⁺⁰ to 24⁺⁶) and third trimester visits (week 32⁺⁰ to 34⁺⁶): At these visits the same data collected at baseline will be obtained. If the patient is, however, admitted for pre-eclampsia before the third visit, the collection will follow the pre-eclampsia diagnosis at admission including treatment offered, length of hospitalization and management.

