- (c) At delivery data to be collected will include gestational age at admission, vital signs, indication for delivery, type of delivery, compliance with protocol, blood for CBC, LFT, and the biomarkers of interest. Post-delivery, discharge vitals, antihypertensive treatment on discharge will be collected.

(d) Exit interview: patient will be called to check for any relevant ADR.

8. Data Management and Analysis plan

Data management:

Upon randomization, research coordinators will be responsible for data collection using approved CRFs. To maintain patient confidentiality, study document such as signed informed consent, and CRFs will be stored in locked cabinets, excel file containing patient identifiable information will be password protected, and all data including patient clinical information and research laboratory results will be entered into the clinical trial management software using patient generated study ID number.

Data analysis:

Descriptive data: Numerical data will be presented as mean and standard deviation where normally distributed or median and range where it's not normally distributed. Categorical data will be presented as frequency and percentages. The percentage of women developed PET will be compared between the intervention and control group using chi square test.

Quantitative data between two arms will be analyzed using either "Unpaired t test or Mann Whitney U test depending on normality of the data distribution". Also, outcomes measured at different time points should be statistically analyzed both within and between groups using repeated measure ANOVA statistical method followed by appropriate multiple comparison tests. All P values presented will be two-tailed. A multivariate logistic regression will be employed to assess the association between metformin use and PET adjusting for confounding factors such as patient demographics (age, GA at delivery, history of risk factors of PET\mentioned above) and co-morbidities such as DM, the dose of metformin, the need to use of antihypertensive drugs, including duration of treatment and any other medications. P values <0.05 will be considered as statistically significant. All Statistical analyses will be done using statistical packages SPSS 22.0 (SPSS Inc. Chicago, IL) and Epi-info (Centers for Disease Control and Prevention, Atlanta, GA) software.

9. Anticipated results and evaluation criteria

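### Repeated-measures ANOVA does not fit the Aim 2 biomarker sampling: pre-eclampsia moves the third collection, and the SAP does not say which time point an admission sample belongs to

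*SAP*

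**What the plan says.** Section 3, Aim 2, objective 2 sets the comparison: "A comparison of the PIGF/sFlt-1 ratio PET in patients who received metformin versus standard care group".

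Section 8, Data analysis, gives the method for repeated outcomes: "outcomes measured at different time points should be statistically analyzed both within and between groups using repeated measure ANOVA statistical method", followed by multiple comparison tests. The same paragraph also has a general rule, "Quantitative data between two arms will be analyzed using either" an unpaired t test or a Mann-Whitney test. It does not say which of the two approaches is the main one for the biomarkers. It gives no rule for missing samples and no term for gestational age at sampling.

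The sampling schedule is described in several places:

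- Section 5, Collected data: "5 ml blood sample will be collected at baseline, second and third trimester and after delivery".
- Section 7, opening paragraph: "one at baseline, and one at each following trimester/visit and admission/s".
- Section 7(b) places the third-trimester visit at 32+0 to 34+6 weeks, then adds: "If the patient is, however, admitted for pre-eclampsia before the third visit, the collection will follow the pre-eclampsia diagnosis at admission".
- Section 7(c) lists the biomarkers again at delivery.

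Two further statements bear on who is analysed. The design paragraph of section 5 promises an intention-to-treat analysis. Section 5, Randomization and initiation of the study, removes all data of a woman who drops out.

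**The concern.** Classical repeated-measures ANOVA assumes that every woman is measured on the same fixed occasions, and it leaves out a woman with any value missing. The data described in section 7 do not have that form. The third collection depends on PET, which is the outcome that metformin is meant to reduce. Section 9 also expects sFlt-1, VEGF and PlGF to be altered in women with PET. So the women whose third sample may be absent or mistimed are those expected to have the most abnormal values, and the plan expects more of them in the control arm.

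Aim 2 asks whether metformin changes the ratio. The answer could depend on an unwritten choice about where admission samples go, and that choice would be made after the data are in. A missing third sample could also cost a woman's valid baseline and second-trimester values.

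**Working it through.** **Plan's own figure.** The SAP gives no sample size, variance or missing-sample rate for the biomarkers, so there is no biomarker figure to reproduce. Its only size calculation is for PET incidence: 172 per arm, raised to 207. A two-sided 5% test of 11.3% against 3% with 80% power and a continuity correction gives 174, close to the stated 172.

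**Inputs from the SAP (section 6).** PET risk p is 0.113 in control and 0.03 on metformin, with 207 women per arm. The arm differences below do not depend on arm size; the counts of women do.

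**Assumptions, not in the SAP.** PET shifts the log ratio by 1 SD. A fraction f of PET women lack a third sample that counts. PET women with and without that sample have the same mean shift. The arm difference considered is only the part that runs through PET.

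**Reading A: the admission sample does not count, so the woman is dropped.**

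With nobody dropped, the arm difference is (0.113 − 0.03) × 1 SD = 0.083 SD.

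Among women with complete sets, the PET share in an arm is p(1 − f) / (1 − p f). For f = 0.4:

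- control: 0.0678 / 0.9548 = 0.0710
- metformin: 0.018 / 0.988 = 0.0182
- difference: 0.0528 SD

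Expected PET cases are 207 × 0.113 = 23.4 in control and 207 × 0.03 = 6.2 on metformin. Women dropped are f times these counts.

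| f | PET women dropped, control v metformin | Difference among complete sets | Share kept |
|---|---|---|---|
| 0 | 0 v 0 | 0.083 SD | 100% |
| 0.2 | 4.7 v 1.2 | 0.068 SD | 82% |
| 0.4 | 9.4 v 2.5 | 0.053 SD | 64% |
| 0.6 | 14.0 v 3.7 | 0.036 SD | 44% |

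The loss applies at any visit where PET women differ by 1 SD, because a dropped woman's earlier values go too.

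**Adding a direct drug effect.** Suppose metformin also shifts the log ratio by 0.30 SD in every woman (an assumed figure). The total is 0.383 SD, and complete sets keep 0.368, 0.353 or 0.336 SD, which is 96%, 92% or 88%.

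**Scale.** The minimum detectable difference at 80% power with 207 per arm is (1.960 + 0.842) × √(2/207) = 0.275 SD. The bias in the table is 0.083 − 0.068 = 0.015 SD up to 0.083 − 0.036 = 0.047 SD.

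**Precision.** Let m be the share of samples missing at each visit at random, and k the number of post-baseline samples needed. The complete-set share is (1 − m)^k, and m is again assumed.

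- m = 5%, k = 2: 187 of 207 women kept
- m = 10%, k = 2: 168 of 207 kept
- m = 20%, k = 3: 106 of 207 kept

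Compared with using every available third-visit sample, the standard error at that visit rises by about 3%, 5% and 25% respectively.

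**Reading B: the admission sample fills the third slot.** Nobody is dropped for this reason, so the table does not apply. The slot then mixes scheduled values with values at PET diagnosis at other gestational ages, and does so unequally by arm. The SAP gives nothing from which to size this.

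**The case against.** The strongest reply is that nothing in the SAP says women with incomplete sets are excluded. That follows only from the classical form of the method. The t test and Mann-Whitney test in the same paragraph need no complete set and could serve objective 2. This stands in part. But section 8 still sends outcomes measured over time to ANOVA, and neither simple test settles where an admission sample belongs.

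A second reply is that the illustration assumes the arm effect runs wholly through PET. Section 9 reasons the other way: metformin acts on sFlt-1 and thereby lowers PET. This stands. With a direct effect the proportional loss is much smaller, as shown above, and the absolute bias is small beside the detectable difference.

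A third reply is that blood is still taken at admission and at delivery, so a sample may be mistimed rather than lost. This also stands. The text supports a change in when the third sample is taken more firmly than a change in whether it is taken.

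Three stronger readings are tempting and should be resisted.

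- A reader might infer that ANOVA discards up to 20% of women. The 20% in section 6 is a sample-size allowance for dropout, not a rate of missing samples. The removal rule in section 5 deletes dropouts' data under any model.
- A reader might add the two harms together. For any one woman, dropping and mistiming are alternatives.
- A reader might infer that within-arm change will be taken as evidence of a drug effect. The SAP plans both within-group and between-group analyses and does not say so.

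**Conclusion.** The point holds as a mismatch between the stated method and the stated data collection, together with a missing rule for admission samples. It should be corrected. It concerns the biomarker aim and leaves the chi-square comparison of PET incidence untouched.

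The between-arm comparison of the ratio can be biased and less precise. The documents do not show that it will be. For a 1 SD PET effect and assumed loss of 20% to 60% of PET women's third samples, the bias is 0.015 to 0.047 SD towards no difference. It is zero if no PET case lacks the sample. The precision loss is about 3% to 25% under the assumed missing rates. The harm from counting admission samples as third-visit values cannot be sized from the SAP.

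**What to change.** In section 8, replace repeated-measures ANOVA for the biomarkers with a linear mixed model on the log ratio, and likewise on log sFlt-1, log PlGF and log VEGF. Analyse women by assigned arm and use every available scheduled sample. Include arm, visit, arm by visit, the baseline log value and gestational age at sampling. Take the between-arm ratio of geometric means with its 95% confidence interval at each visit as the treatment comparison, not within-arm change.

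In section 7(b), state that PET-admission samples are kept apart from the scheduled third visit and analysed separately. Add two sensitivity analyses:

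- one that includes admission samples at their actual gestational age;
- one that allows for third samples missing because of PET or early delivery. The mixed model assumes data are missing at random, and that may fail for exactly these women.

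In section 5, replace the removal rule with retention of data collected before dropout, where consent allows. As written it conflicts with the intention-to-treat statement, and no choice of model can recover those women.

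The cost is wording, slightly more analysis work and reliance on the missing-at-random assumption. SPSS, already named in section 8, fits mixed models, and no extra sampling is needed.

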A decreased level of VEGF and PIGF free form has been observed that has been attributed to their blockade by the increased level of sFlt-1 in pre-eclamptic women (29,41,42). Indeed, the introduction of sFlt-1 to a pregnant rat led to hypertension and proteinuria similar to that seen in PET women (42). Furthermore, an altered ratio of serum PIGF/sFlt-1 has been found to be associated with PET diagnosis and disease severity (43–46). Indeed, there is now a drive to use this ratio in screening women at risk of PET but most of the data were generated in late pregnancy rather than in early pregnancy – a time when interventions have been shown to have maximum impact (46). It would seem from this greater understanding of the underlying physiological changes in women that develop PET that any interventions that have the potential to alter this milieu are more likely to be successful.

Very recently a double-blind, placebo-controlled trial, that randomly assigned pregnant women without diabetes who had a body-mass index of more than 35 to receive metformin, at a dose of 3.0 g per day, or placebo (225 women in each group) from 12 to 18 weeks of gestation until delivery showed a significant reduction in the incidence of PET in those who received metformin (47). Since metformin is now frequently prescribed to obese type II diabetic women and gestational diabetics with poor glycemic control on diet, it is hypothesized in those at risk of PET, metformin will not only reduce the incidence of PET but will modify the PIGF/s-Flt-1 ratio in favor of normal pregnancies.

2. Study aims and goals

Aim 1: To investigate whether the administration of metformin to women at high risk of pre-eclampsia will reduce the incidence.

Aim 2: To determine accuracy of the ratio of PIGF/sFlt-1 in predicting PET and the effect of metformin on this ratio

Aim 3: To study the molecular mechanisms and signaling pathways associated with increased levels of sFlt-1 and PET

3. Objectives of this study

Aim 1: To investigate whether the administration of metformin to women at high risk of pre-eclampsia will reduce the incidence.

The objectives under this aim will include

1. A comparison of the incidence of pre-eclampsia and its severity in women receiving metformin versus standard care,
2. A comparison of the GA at delivery, maternal and fetal outcomes in those receiving Metformin versus standard care,
3. A comparison of the timing of onset of PET between the two groups and

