Metformin has been in use since 1957 but its specific mechanism of action is unknown (62). Previously, AMPK-activation has been identified as one of the mechanisms by which it exerts its angiogenic activity (63). However, metformin does not activate AMPK directly. Instead, AMPK activation is a result of metformin inhibition of the mitochondrial respiratory chain complex 1 (reviewed in (64,65)). Apart from diabetes, it has also been implicated in the prevention of cancer, adverse outcomes in women with PCOS and most recently in the prevention of PET (reviewed in (66)). In an ex-vivo study using primary placental tissue from PET placentas, metformin treatment resulted in reduced endothelial dysfunction, enhanced vasodilatation and induced angiogenesis by sFlt-1 and endoglin reduction possibly at the mitochondrial level (30). Despite these, the exact mechanism behind its role in the prevention of PET remains poorly understood. Further clarification of how metformin decreases the incidence of pre-eclampsia needs to be examined. Here we plan to explore altered maternal serum levels of sFlt-1, PIGF and VEGF in pregnant women using metformin.

5. Study design and methodology

This is an open label, randomized control trial (RCT) in which high risk for pre-eclampsia pregnant subjects will be randomly assigned to either an intervention group (metformin 1 gm twice daily plus aspirin 100 mg per day and standard of care) versus control group (aspirin 100 mg per day and standard of care) that will be administered between 11^{+0} to 13^{+6} weeks of gestation until delivery (appendix 1). Only women at high risk of pre-eclampsia as defined by the ACOG practice bulletin will be included (see inclusion criteria). Patient assignment will not be blinded as control group will not be given a placebo; the data will be analyzed on an intention to treat basis. Enrolled subjects will be followed throughout pregnancy and up to 30 days post-delivery (as per hospital practice).

Study definitions:

High risk of preeclampsia:

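### The adjusted logistic model for PET includes metformin dose, which is part of the exposure, and other adjusters not limited to values before randomisation

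*SAP*

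**What the plan says.** Section 8 (Data analysis) compares the percentage with PET between groups by chi-square. It then adds the only adjusted analysis of PET: "A multivariate logistic regression will be employed to assess the association between metformin use and PET". The covariate list opens with the words "adjusting for confounding factors such as patient demographics (age, GA at delivery", and then names past PET risk factors. Further on it gives "co-morbidities such as DM, the dose of metformin, the need to use of antihypertensive drugs, including duration of treatment", and it closes with a catch-all for other drugs. No time of measurement is given for any term.

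Other parts of the SAP bear on these terms:

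- **Dose.** Section 5 assigns one fixed regimen to the intervention arm, "metformin 1 gm twice daily plus aspirin 100 mg per day and standard of care"; controls are assigned no metformin. Of a control woman who starts metformin for gestational diabetes, section 5 (Randomization and initiation) says "she will be moved to intervention group and analyzed as late started".
- **GA at delivery.** Section 3 makes it an Aim 1 outcome: "A comparison of the GA at delivery, maternal and fetal outcomes in those receiving Metformin versus standard care". Section 7(c) collects, at delivery, "gestational age at admission, vital signs, indication for delivery, type of delivery".
- **Diabetes.** The exclusion criteria rule out type 1 and type 2 diabetes and early gestational diabetes.
- **Antihypertensives.** Hypertension is part of the PET definition in section 5, and section 7(c) records antihypertensive treatment at discharge.
- **Analysis principle.** Section 5 states that "the data will be analyzed on an intention to treat basis".

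**The concern.** A confounder influences both exposure and outcome. Metformin dose is the exposure measured on a finer scale. With use and dose in one model, the use coefficient no longer answers Aim 1, whether giving metformin lowers PET incidence. It compares users with non-users at the same dose, a contrast for which the trial has almost no data.

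The other terms are a matter of timing. Measured in this pregnancy after randomisation, GA at delivery is an outcome and antihypertensive use is partly a consequence of PET. Given the exclusions, diabetes can essentially appear only after entry. Adjusting for such variables costs precision and may change what is estimated.

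At stake is the SAP's only adjusted estimate for PET. It is judged at the same 0.05 level as the chi-square test and could be uninterpretable beside it.

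**Working it through.** **1. The plan's own figures (section 6).** PET risks are 3% and 11.3%, with 172 women per arm.

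- OR = (0.03/0.97)/(0.113/0.887) = 0.0309/0.1274 = 0.24, as stated.
- Sample size at 80% power and two-sided 5%: 151 per arm without continuity correction and 174 with it. The stated 172 is close to the latter.
- Expected events: 172 × 0.03 = 5.2 and 172 × 0.113 = 19.4, total 24.6.
- Arm-only SE(log OR) = √(1/5.16 + 1/166.84 + 1/19.44 + 1/152.56) = √0.258 = 0.51.

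**2. Redundancy of use and dose.** If every user takes 2 g daily, dose = 2 × use and the design matrix is singular (500 of 500 simulated trials). Otherwise let p be the proportion of users, and m and v the mean and variance of dose among users. The variance inflation factor is 1/(1 − r²) = 1 + (1 − p)m²/v. The dose distributions below are assumptions, because the SAP gives none.

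- 10% of controls start metformin at 1, 1.5 or 2 g with equal chance, metformin arm all at 2 g: p = 0.55, m = 1.955, v = 0.0358, so 1 + 0.45 × 3.820/0.0358 ≈ 49 (50 in simulation).
- 20% of controls start: p = 0.60, m = 1.917, v = 0.0625, so 1 + 0.40 × 3.674/0.0625 ≈ 24.5 (25 in simulation).
- No switching, 20% of users on 0.5, 1 or 1.5 g: p = 0.50, m = 1.8, v = 0.193, so 1 + 0.50 × 3.24/0.193 ≈ 9.4 (9.6 in simulation).
- No switching, 50% of users reduced: 1 + 0.50 × 2.25/0.333 ≈ 4.4, which multiplies the SE by about 2.1.

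**3. Simulated logistic fits**, 172 per arm. SEs are medians over usable fits. Switched controls count as users, following the late-started rule.

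| Assumption | Fits failing | SE of use | Ratio to arm-only SE |
|---|---|---|---|
| 10% / 20% of controls switch, keep control risk | 28% / 8% | 2.3 / 1.7 | 4.5 / 3.3 |
| 10% / 20% switch, full benefit | 70% / 50% | 2.4 / 2.3 | 4.7 / 4.5 |
| No switching, 20% of users reduced | 49 of 500, and 115 more unstable | 1.59 | 3.1 |
| No switching, 50% / 70% of users reduced | not tabulated | 1.28 / 1.17 | 2.5 / 2.3 |
| Adherence uniform from 10% to 100% | not tabulated | 1.12 | 2.2 |

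**4. Direction of the use coefficient**, with 10% / 20% of controls switching.

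| PET risk in switched controls | Large-sample OR for use | Trials with significant harm |
|---|---|---|
| 11.3% (no benefit) | 5.5 / 4.9 | 15% / 19% |
| 7% | not tabulated | 6% / 7% |
| 3% (full benefit) | 0.24 | 1% / 0.5% |

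**5. GA at delivery and antihypertensive use**, taken as measured after randomisation and dependent on PET only.

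- Assuming delivery 2.6 weeks earlier with PET (SD 1.8) and antihypertensives in 80% with PET against 10% without, the share of significant trials falls from 86% to 57% (SE 0.69).
- With 1.5 weeks and 60% against 15%, it falls from 87% to 79% (SE 0.56).
- The large-sample OR stays at 0.24 in both.
- It moves to 0.29 or 0.36 only if metformin is also assumed to lower antihypertensive use in women without PET from 10% to 7.5% or 5%. The SAP gives no such figure.

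**6. Events per coefficient.** Eight adjusters are named (age, GA at delivery, risk-factor history, diabetes, dose, antihypertensive need, duration, other medications). With use, that makes nine terms if each takes one coefficient: 24.6/9 = 2.7 events each. Diabetes and other medications were not simulated.

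**The case against.** **Some terms may be meant as baseline values.** The background section uses GA at delivery for a previous affected pregnancy, and chronic hypertension is a risk factor for entry, so antihypertensive need could be pre-existing. Both readings are possible and the text does not settle them. Neither helps dose.

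**Dose may mean dose taken.** Section 5 plans pill counts, so a model with no dose variation at all is unlikely. This stands. Exact collinearity is the limiting case, and with widely varying intake the SE ratio is nearer 2. A reader might take the switching scenarios to set a floor of, say, 2.7 times; the wider-variation cases give 2.2 to 2.5.

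**A reader might infer that the model will show harm.** The documents do not support that. The ORs near 5 require switched controls to gain nothing while the whole metformin arm takes 2 g. Even then the use coefficient is an extrapolation to zero dose. Combining use and dose from the same fits, 2 g against none, gives 0.27 / 0.30, a benefit.

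**A reader might infer that GA and antihypertensive use bias the OR.** That needs an effect of metformin on them other than through PET, which the SAP does not state.

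**The list is open-ended.** Its terms may be examples, so nine coefficients are a count of what is named, not a commitment. But an open list chosen after the data are seen is no better with about 25 events.

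**Conclusion.** The model is wrong as written and should be corrected. Putting metformin dose beside metformin use is a specification fault on any reading. The model cannot be fitted if dose does not vary. If it varies, the SE is about 2 to 5 times the arm-only 0.51, with up to about 70% of fits failing. The size rests on assumed switching and dose distributions; the fault does not.

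GA at delivery, diabetes, antihypertensives and other medications are unsuitable adjusters if measured after randomisation, and the SAP must fix their timing. For GA and antihypertensives the demonstrated cost is precision; a shift in the OR is conditional.

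A reader might also infer that the main PET comparison is compromised. The covariate fault does not reach the chi-square test. Whether that test uses randomised arm is a separate conflict between the intention-to-treat statement and the late-started rule.

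**What to change.** In section 8:

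- Make randomised arm the exposure in the logistic model, in line with intention to treat.
- Remove metformin dose, GA at delivery of the current pregnancy, diabetes, and antihypertensives or other medications started after randomisation.
- Adjust only for a short pre-specified list of baseline covariates, for example age, previous PET, and chronic hypertension or baseline antihypertensive use.
- If GA at delivery refers to a previous pregnancy, say so; state which treatment the duration refers to.
- Report GA at delivery as an outcome, and any dose or adherence analysis separately as exploratory.

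The cost is SAP wording only, since section 7(a) already collects age and obstetrical, medical and medication history at baseline. In simulation, arm plus three such covariates kept 86% of trials significant (SE 0.53, 99% of fits converging), at 24.6/4, or about 6, events per coefficient. Covariate prevalences and effects were assumed.

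The downside is that the adjusted model no longer addresses dose or co-medication. With about 5 PET events expected in the metformin arm, the trial could not answer that question anyway.
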